**Title: Transcranial Direct Current Stimulation for Pain Treatment in Gulf War Illness**

**NCT03312920**

**Date: June 20/2017**

## Statistical plan:

### 1. Study Overview and Objectives

The study evaluates the efficacy of transcranial Direct Current Stimulation (tDCS) for managing pain in Gulf War Illness (GWI) veterans. The specific objectives are to determine if tDCS targeting the occipital nerve reduces pain and to identify EEG and rsfMRI-based markers that correlate with pain relief.

### 2. Study Design and Groups

- **Design:** Prospective, double-blind, randomized controlled trial with a parallel-group design. This prevents potential carry-over effects from sham to treatment phases.
- **Groups:**
  - **Active tDCS Group:** Real tDCS targeting the occipital nerve at 1.5mA for 20 minutes.
  - **Sham tDCS Group:** Sham tDCS with a brief current sensation to maintain blinding but no sustained current.

### 3. Sample Size and Power

- **Primary Outcome:** Pain severity on the Visual Analogue Scale (VAS).
- **Secondary Outcomes:** Questionnaire measures (MFIS, PSQI, BDI, PCS, MGPQ, PVAQ) and neurophysiological measures (LEP, EEG, rsfMRI).
- **Sample Size:** 60 participants (30 per group), allowing an 80% power to detect a 1.1 cm difference on the VAS scale (Cohen's d effect size) with a significance level of 0.05. The design anticipates a 10% dropout rate.

### 4. Data Collection Timeline

- **Assessment Points:**
  - **Baseline:** Pre-treatment assessment.
  - **Immediate Post-Treatment:** After the 10 tDCS sessions.
  - **Follow-Up:** 4 weeks, 12 weeks, and 24 weeks post-treatment.

### 5. Data Management

- **De-identification and Confidentiality:** Data will be stored under a de-identified code compliant with HIPAA regulations and protected by a Certificate of Confidentiality. Only authorized personnel will access the data.
- **Data Storage and Disposal:** Data will be stored securely and deleted seven years post-study completion.

### 6. Statistical Analysis Plan

#### A. Primary Outcome Analysis: Pain Severity (VAS)

- **Modeling:** Mixed-effects repeated-measures ANOVA with group (treatment vs. sham) as a between-subjects factor and time (baseline, immediate post-treatment, 4-week, 12-week, 24-week) as a within-subjects factor.
- **Post-Hoc Tests:** Bonferroni-adjusted post-hoc tests will examine specific time points if interaction effects are significant.
- **Intention-to-Treat (ITT) and Per-Protocol Analyses:**
  - **ITT:** Last observation carried forward (LOCF) for missing data.
  - **Per-Protocol:** Include only participants with at least 8 out of 10 therapy sessions completed and no interfering medications.

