The goal of this proposal is to produce long-term modulation of pain pathways leading to a suppression of pain symptoms in Gulf War Illness patients with pain symptoms by delivery of 10 daily sessions (1 session a day, 5 weekdays a week, for a 2 week period) of transcranial Direct Current Stimulation (tDCS) over specific nerves at the back of the head (i.e. the occipital nerve field (C2)). After identifying Gulf War illness patients with pain symptoms using standard measures, we will address the following specific aims:

Aim 1. Produce long-term modulation of pain pathways reflected in a suppression of pain symptoms by administering repeated sessions of real tDCS targeting the greater occipital nerve at the back of the head.

Hypothesis #1: pain symptoms detectable in measures of pain symptoms (e.g. Visual Analogue Scale and other pain scales) will be improved after repeated sessions of real tDCS when compared to sham tDCS.

Aim 2. Produce long-term modulation of pain pathways reflected in resting state Electroecephalography (EEG) after administering repeated sessions of real tDCS targeting the greater occipital nerve at the back of the head.

Hypothesis # 2: EEG resting state activity changes in both the ascending pathways and descending pathway correlate with suppression of pain. A decrease in activity in the pregenual Anterior Cingulate Cortex (ACC), dorsal Anterior Cingulate Cortex (dACC), insula, and somatosensory cortex after the procedure will be less strongly correlated with pain in comparison to the baseline measurement.

Describe previous studies that form the basis for the proposed research:

Gulf War Illness is a chronic and multisymptomatic disorder affecting returning military veterans of the 1990-1991 Gulf war. Pain is a major complaint of Gulf War Illness patients and is a leading cause of disability in veterans diagnosed with musculoskeletal ailments including joint and muscle pain, muscle fatigue, difficulty with lifting objects, and extremity paresthesia's. As a result, the target of the present proposal is the treatment of the pain symptoms, as this is detectable across all Gulf War Illness case classification systems.

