Interestingly, Gulf War veterans with pain symptoms often meet the criteria for fibromyalgia, strongly suggesting an overlap in not only pain symptoms but also in the mechanisms of action. Current treatment options for Gulf War Illness are as diverse as their outcomes. Both pharmacological and non-pharmacological modalities are currently used, but only a small subset of patients benefit and most of the patients remain noncompliant to treatment. As current treatment options generate only moderate improvement, modification of cortical physiology by non-invasive brain stimulation would be a valuable and novel therapeutic approach. Our group has developed a new treatment option using transcranial Direct Current Stimulation (tDCS) for the management of pain in patients with Fibromyalgia (Plazier et al., 2014; Plazier et al., 2015). We demonstrated in a recent study published in Neuromodulation (N = 10) and a follow-up clinical trial published in Brain Stimulation (N = 45) that direct stimulation of some nerves at the back of the head (i.e. the occipital nerve field) of fibromyalgia patients seems to cause an overall beneficial effect on general bodily pain (e.g. bone and joint pain) symptoms and confirmed additional improvement on participants' tender points, quality of life, fatique, and sleep quality (Plazier et al., 2014; Plazier et al., 2015). This effect was maintained within a six-month follow up period. Seventy-six percent of the patients were satisfied or very satisfied with their treatment and 56% of the patients were able to return to work. We further showed that transcranial direct current stimulation (tDCS) can be used to non-invasively modulate these nerves at the back of the head (i.e. occipital nerve field), producing similar results ([name] et al., 2011). Our study showed that stimulation of these nerves at the back of the head (i.e. occipital nerve field) using tDCS over 10 sessions decreased bone and joint pain symptoms by 30% in comparison to baseline and 22% in comparison to sham stimulation in patients diagnosed with fibromyalgia (see figure 4, middle)(Plazier et al. 2015c). These findings are further confirmed by our recent pilot study (N = 15) performing 10 sessions of tDCS targeting the nerves at the back of the head (i.e. occipital nerve field), showing pain suppression of 21% and fatigue suppression of 25% for more than 6 months. In another study by our group, we also showed that this stimulation set up has a direct impact on the latencies of the Laser Evoked Potential (Plazier et al., 2015) and confirmed its impact on joint/muscle pain symptoms in patients with fibromyalgia.

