
Last Revised 01/2016 Page 4 of 22

Given the promising results for pain symptoms in fibromyalgia patients, we aim to explore this treatment option for Gulf War illness patients with pain symptoms

What information do you expect to obtain and how will the obtained knowledge be applied:

To investigate the effects of repeated sessions of tDCS targeting the occipital nerve field on pain symptoms and on global and specific symptoms in GWI participants, we will measure possible changes in symptoms (using questionnaires) and electrophysiological brain activity (resting-state EEG) in a group that receives active tDCS and a group that receives sham tDCS.

The primary outcome measure for pain symptoms will be measured by the Visual Analogue Scale (VAS).

VAS. The Visual Analogue Scale consists of a straight line of 10 cm with the endpoints defining extreme limits such as 'no pain at all' and 'pain as bad as it could be'. The patient is asked to mark his widespread muscle pain level on the line between the two endpoints. The distance between 'no pain at all' and the mark then defines the subject's pain. VAS will be assessed for pain severity. It has been used to measure symptom relief and treatment satisfaction. Several studies have demonstrated that the VAS is sensitive to treatment effects (Haefeli & Elfering, 2006). The VAS has been found to correlate positively with other self-reporting measures of pain intensity. In addition, the difference in pain intensity measured at two different points of time by VAS represents the real difference in magnitude of pain which seems to be the major advantage of this tool compared to others. This will be performed both during Phase I as well as during Phase II after 4-weeks, 12-weeks, and 24-weeks of treatment.

The secondary outcome measures will include measures of of global change as well as changes in specific symptoms of interest related to the Center for Disease Control (CDC) clusters, as GWI is a complex disease with multiple symptom manifestations: Cluster A by the Modified Fatigue Impact Scale (MFIS) and the Pittsburgh Sleep Quality Index (PSQI); Cluster B, mood and cognition, will be assessed by Beck Depression Inventory (BDI); and Cluster C by the Pain Catastrophizing Scale (PCS), McGill Pain Questionnaire (MGPQ), and Pain Vigilance and Awareness Questionnaire (PVAQ).

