**Deviation statistical plan:**

The study was unfortunately disrupted due to the impact of COVID-19, which led to its discontinuation. Consequently, we have been limited in our ability to collect and analyze comprehensive data, and are currently only able to report descriptive statistics. We acknowledge that this is a limitation in our findings, and we are exploring potential avenues to resume the study and gather more robust data in the future.

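### The trial is sized on one 1.1 cm VAS difference tied to no visit, but the implied primary test is a directionless 4-df group-by-time interaction with baseline as a time level

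*SAP*

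**What the plan says.** - **Sizing.** SAP section 3 gives VAS pain severity as the primary outcome and 30 participants per group, "allowing an 80% power to detect a 1.1 cm difference on the VAS scale". It attaches no visit, SD or within-person correlation to that figure.
- **Model.** SAP section 6A specifies a repeated-measures ANOVA with group as the between-subjects factor and "time (baseline, immediate post-treatment, 4-week, 12-week, 24-week) as a within-subjects factor".
- **Gate.** The same section adds: "Bonferroni-adjusted post-hoc tests will examine specific time points if interaction effects are significant". It does not say which term of the model is confirmatory. For the questionnaires, section 6B does name the interaction.
- **Protocol.** Aim 1 is to "Produce long-term modulation of pain pathways reflected in a suppression of pain symptoms". Hypothesis 1 is that pain measures "will be improved after repeated sessions of real tDCS when compared to sham tDCS", which fits any post-treatment visit. The VAS paragraph of the Protocol Summary lists occasions without ranking them: "This will be performed both during Phase I as well as during Phase II after 4-weeks, 12-weeks, and 24-weeks of treatment".
- **Visits.** The protocol's session list (sessions 12 to 15) has VAS at 1, 4, 12 and 24 weeks after stimulation. SAP sections 4 and 6A omit the 1-week visit.
- **Status.** The deviation note that closes the SAP says the investigators "are currently only able to report descriptive statistics".

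**The concern.** The power statement concerns one active-minus-sham difference. The implied test asks something else: whether the difference between the groups varies in any way over five occasions, one of them before treatment.

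A significant answer does not say which arm did better, when, or by how much. After a non-significant answer, the plan calls for no visit-level test. Nor does the test single out a lasting effect, which is what Aim 1 seeks. The tDCS pilot cited in the protocol's account of previous studies also points to a lasting effect: "showing pain suppression of 21% and fatigue suppression of 25% for more than 6 months".

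At stake is whether an inferential VAS result would answer Hypothesis 1 on the scale on which the trial was sized.

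**Working it through.** **1. The plan's own figure.** The 60 can be neither reproduced nor refuted, because no SD is given. Taking 60 less 10% (27 per arm) and a two-sided two-sample t-test at 0.05, 80% power needs d = 0.777, so SD = 1.1/0.777 = 1.42 cm. With 30 per arm it needs d = 0.736 (SD about 1.50 cm), and the base-case results below move by less than one point. Section 3 also labels the 1.1 as a Cohen's d. Read that way, the same t-test has 98% power with 27 per arm, which does not fit the stated 80%.

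**2. Degrees of freedom.** Two groups and five times give (2-1) x (5-1) = 4 for the interaction.

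**3. What the interaction responds to.** Under compound symmetry with correlation r, the noncentrality is (n/2) x S/(1-r). Here S is the sum of squared deviations of the five standardised group differences from their mean.
- Effect d at all four post-treatment visits: the mean is 0.8d, so S = (0.8d)^2 + 4(0.2d)^2 = 0.8d^2.
- Effect d at one visit only: the mean is 0.2d, so S = (0.8d)^2 + 4(0.2d)^2 = 0.8d^2.

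The two are equal, so the power is identical.

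**4. Base case.** Inputs: n = 27 per arm and d = 0.777 (from step 1); r = 0.3/0.5/0.7, compound symmetry and complete data (all assumed).
- Interaction, sustained effect: S = 0.8 x 0.777^2 = 0.483. The noncentrality is 13.5 x 0.483/(1-r) = 9.3/13.0/21.7 on 4 and 208 df.
- One baseline-adjusted visit: noncentral t with d x sqrt(n/2)/sqrt(1-r^2) = 2.99/3.30/4.00 on 51 df.
- Baseline-adjusted average of the SAP's four post-treatment visits: noncentral t with mean effect x sqrt(n/2)/sqrt((1+3r)/4 - r^2) = 4.60/4.66/5.35 on 51 df.

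Power in %, at r = 0.3/0.5/0.7:

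| Effect pattern | 4-df interaction | Immediate visit, adjusted | Average of four, adjusted |
|---|---|---|---|
| Sustained | 67/83/97 | 83/90/97 | over 99 at each |
| Waning (100/75/50/25% of d) | 55/71/92 | 83/90/97 | 80/82/91 |
| First two visits only | 86/96/over 99 | 83/90/97 | 62/63/75 |
| Last two visits only | 86/96/over 99 | no power | 62/63/75 |

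**5. Sensitivity, sustained effect.** With d = 1.1 the interaction has 95/99/over 99%. With SD 2.0 cm (d = 0.55) the interaction has 36/50/75%, one adjusted visit 55/63/79% and the adjusted average 89/90/96%.

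**6. Value of baseline as a covariate.** For a single visit, the variance relative to a change score is (1-r^2)/(2(1-r)) = (1+r)/2 = 0.65/0.75/0.85. That is 35/25/15% lower.

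**The case against.** **The plan already has a decision rule.** Section 6A sets out a conventional sequence: overall interaction, then Bonferroni-adjusted visit tests. That stands. A reader might infer that nothing indicates how Hypothesis 1 would be judged, but that goes too far. The sequence can be inferred; what is missing is a stated confirmatory term and a visit or contrast for the 1.1 cm.

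**The trial is not shown to be underpowered.** This also stands. A reader might take the lower figures above as proof of a shortfall. The documents do not support that: they give no SD, no correlation and no sizing test. In the base case the interaction has 83% and 97% power at correlations 0.5 and 0.7, and if 1.1 is a Cohen's d there is no shortfall. Under purely serial correlation with the covariance modelled (assumed baseline-to-immediate correlation 0.89 to 0.97), a multivariate test of the interaction and both single contrasts exceed 99% for a sustained effect, so there is no power to gain.

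**The fitted model can supply visit estimates.** True, and nothing forbids reporting them. But nothing requires them after a non-significant interaction.

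**A lighter remedy might do.** One could keep the ANOVA and name the post-treatment average minus baseline. Replacing the covariate variance in step 4 with (1+3r)/4 + 1 - 2r, on 52 df, gives 85/94/over 99% for a sustained effect. For a waning effect it gives about 46/60/82%, against 80/82/91% with baseline as a covariate. Using baseline through differences is valid, but the covariate is more than a matter of taste.

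**The study stopped.** The deviation note makes the consequence conditional. It also says that ways to resume are being explored, so the point is not moot.

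**Conclusion.** The point holds as a mismatch between what the trial was sized on and what the implied primary test examines. It rests on the text alone: one 1.1 cm difference tied to no visit, a five-level time factor that includes baseline, and visit tests only after a significant interaction. The equal-power result in step 3 additionally needs compound symmetry.

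The power figures illustrate the size of the mismatch and are conditional on the assumed SD, correlation and effect pattern. For a sustained effect in the base case, the interaction falls below 80% only at the lowest correlation considered. No single contrast is best under every pattern: effects confined to two visits favour the interaction over the average.

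The amendment should be made before any further inferential analysis. While reporting stays descriptive, no current VAS result depends on it. Confidence is medium.

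**What to change.** Issue a dated SAP amendment before any further inferential analysis:

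1. Model post-treatment VAS with baseline VAS as a covariate, plus group, visit and group-by-visit.
2. Report the adjusted active-minus-sham difference at every visit with a 95% CI, whatever the interaction shows.
3. Have the sponsor name one 1-df primary contrast, either a single visit or the adjusted average over listed visits, and state that the 1.1 cm refers to it. The average suits a sustained effect. The immediate visit is at least as powerful in the base case if the effect wanes, but misses a late-only effect.
4. Reconcile the protocol's 1-week VAS visit with the SAP's visit list, and say whether it enters the model and any average. The calculations above use the SAP's four post-treatment visits.
5. Label any model estimate from data already collected as post hoc.

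**Cost.** No new data are needed, and the covariate uses one degree of freedom. The real price is in item 3: a 1-df contrast can lose power if the effect is confined to some visits. In the base case the average drops to 62/63/75% when only two visits carry the effect, against 86/96/over 99% for the interaction.

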Participant's Review of Inclusion/Exclusion Criteria: Prospective participants will initially review general inclusion and exclusion criteria about the study on the recruiting materials where there is contact information to contact a researcher for more detailed information about the study.

Interested individuals will be screened through a phone screen script. Their continued interest in the study confirms that they have met (via self-report) basic inclusion/exclusion criteria.

Administration of Consent Form: When the Consent form is administered, participants will have already acknowledged that they have met the above criteria and have expressed continued interest in participating in the study. If, at that time, they feel that they do not meet these criteria, or have specific questions about these criteria, they will be asked to inform the research team member administering the consent form. If they again meet these criteria to the best of their knowledge, a second set of study screening procedures will be administered to evaluate whether or not they qualify for the study. All of the remaining screening and study procedures described hereinafter will be administered only if the participant has provided consent to participate (i.e., signed the consent form).

It is an eleven day study with four follow-up sessions: 1 week, 4 weeks, 12 weeks and 24 weeks after the last day of stimulation.

Session 1: Pre-tDCS Assessment (approximately 3 hours)

Assessment: At [name]'s lab, The following questionnaires/tests will be administered:

- 1. VAS. The Visual Analogue Scale
- 2. MFIS. Modified Fatigue Impact Scale
- 3. PSQI. Pittsburgh Sleep Quality Index
- 4. BDI. Beck Depression Inventory
- 5. PCS. Pain Catastrophizing Scale
- 6. MGPQ. McGill Pain Questionnaire
- 7. PVAQ. Pain Vigilance and Awareness Questionnaire

In addition, changes in electrophysiological brain activity will be measured using resting-state EEG.

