## B. Secondary Outcome Analysis

- **Questionnaires:** MFIS, PSQI, BDI, PCS, MGPO, and PVAQ will be assessed using repeated-measures ANOVA to evaluate time × group interactions.
- **Neurophysiological Markers:**
  - **LEP:** N2P2 amplitude and latency will be assessed using repeated-measures ANOVA to evaluate group (treatment vs. sham) × time (baseline vs. immediate post-treatment) interactions. Correlations between VAS changes and N2P2 amplitude differences will be analyzed with Pearson correlations.
  - **EEG:** sLORETA contrast maps will analyze voxel-by-voxel comparisons (pre- vs. post-tDCS) to determine active vs. sham differences. Randomized statistical thresholding (5000 permutations) will correct for multiple comparisons.
  - **rsfMRI:** Seed-based functional connectivity analyses will target key regions (dACC, pgACC, amygdala, and insula). Group-level comparisons (treatment vs. sham) will assess changes from baseline to post-treatment and correlate with VAS scores to evaluate pain reduction prediction.

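### The primary model treats baseline VAS as a time level rather than a covariate, which costs precision (not validity) in every active-minus-sham comparison

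*SAP*

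**What the plan says.** SAP 6A specifies a mixed-effects repeated-measures ANOVA for the VAS, with group as the between-subjects factor and "time (baseline, immediate post-treatment, 4-week, 12-week, 24-week) as a within-subjects factor". Visit-level comparisons follow, with Bonferroni adjustment, only if the interaction is significant. No covariate is named, and nothing sets a common baseline mean for the two arms.

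For the secondary questionnaires, SAP 6B says that they "will be assessed using repeated-measures ANOVA to evaluate time" by group interactions. It lists no time levels for them, so treating their model as the same form as 6A is an inference.

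The Protocol's Session 1 pre-tDCS assessment includes "The Visual Analogue Scale" and all six questionnaires. Its account of the stimulation sessions places random assignment after that assessment, so each baseline score precedes randomisation.

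SAP section 3 describes the sample of 30 per group as "allowing an 80% power to detect a 1.1 cm difference on the VAS scale", "with a significance level of 0.05". It states no SD, correlation, sidedness or test. The closing deviation note says that the trial was discontinued because of COVID-19, that only descriptive statistics can be reported, and that resumption is being explored.

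**The concern.** When baseline is one of the responses and each arm has its own baseline mean, the group-by-time interaction compares changes from baseline. A change score carries the full noise of the baseline measurement. A covariate adjustment removes only the part of the outcome that baseline predicts, and so leaves less residual variance. If a post-hoc test instead compares raw scores at one visit, baseline is not used at all. Adjustment is more precise in either case.

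What is at stake is power in a trial of 60 people, from data that are collected anyway. A second consequence applies within any one trial. With rho below 1, a change score over-corrects a chance baseline imbalance, so the arm that happens to start higher tends to show more improvement through regression to the mean.

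**Working it through.** **Inputs.** From SAP section 3: 30 per group, target 1.1 cm, 80% power, alpha 0.05. Assumed: two-sided testing, and rho from 0.3 to 0.7.

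**The plan's own figure.** With no SD given, the 80% can be back-solved but not reproduced independently. A two-sample noncentral t with 30 per group and two-sided 0.05 reaches 80% at a standardised difference of 0.736, so SD = 1.1/0.736 = 1.495 cm (1.52 cm by the normal approximation). With 27 per group, after the 10% dropout, the implied SD is 1.42 cm. The powers below are the same at 27 if the SD is back-solved there.

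**Variance per person.**
- Change from baseline: 2(1-rho)SD²
- Raw score at one visit: SD²
- Baseline as covariate: (1-rho²)SD²

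The ratio of adjusted to change variance is (1-rho²)/[2(1-rho)] = (1+rho)/2, below 1 for every rho below 1. The ratio of adjusted to raw is 1-rho², below 1 for any non-zero rho. At rho 0.5 both equal 0.75.

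**Power for one visit, two-sided 0.05.** The result depends on which contrast the stated 80% was meant for, and the SAP does not say.

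| rho | If 80% is for a raw score: change | same: adjusted | If 80% is for change: change | same: adjusted |
|---|---|---|---|---|
| 0.3 | 66% | 84% | 80% | 93% |
| 0.4 | 72% | 86% | 80% | 92% |
| 0.5 | 80% | 90% | 80% | 90% |
| 0.6 | 88% | 94% | 80% | 88% |
| 0.7 | 95% | 97.5% | 80% | 86% |

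If the post-hoc tests compare raw scores, the planned power is 80% at every rho and the adjusted power is the third column. At Bonferroni 0.05/4 and rho 0.5, power goes from 61% to 76%. A simulation of 20,000 trials at rho 0.5 (SD 1.52) gave 79-80% for the change contrast, 79% for the raw contrast and 88% with baseline as covariate.

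**Power for the test the SAP runs first.** This is the 4-df group-by-time interaction. Assume equal correlation between all visits, and let d be the four post-treatment effects. With S1 = sum of d and S2 = sum of d², the noncentrality is
- planned: [15/(SD²(1-rho))] × [S2 - S1²/5]
- adjusted, joint test of the four differences: [15/(SD²(1-rho))] × [S2 - rho·S1²/(1+4rho)]

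At rho 0.5, SD² = 2.236, so the multiplier is 15/1.118 = 13.42 and rho/(1+4rho) = 1/6. Power is from a noncentral F on 4 and 232 df, used as an approximation for both.

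| Effect at the four visits (cm) | S2 | S1² | Noncentrality, planned → adjusted | Power, planned → adjusted |
|---|---|---|---|---|
| 1.1 at all four | 4.84 | 19.36 | 12.99 → 21.65 | 83% → 97% |
| 1.1, 0.8, 0.4, 0 | 2.01 | 5.29 | 12.77 → 15.14 | 82% → 89% |
| 1.1, 0, 0, 0 | 1.21 | 1.21 | 12.99 → 13.53 | 83% → 85% |

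At rho 0.7 the planned power is already about 97% for all three shapes, and the gain is about 0 to 2 points.

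**Chance imbalance.** The SE of the baseline difference is 1.495 × sqrt(2/30) = 0.386 cm. An imbalance of one SE shifts the change contrast by (1-0.5) × 0.386 = 0.19 cm at rho 0.5, which is 18% of 1.1 cm.

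**The case against.** Repeated-measures ANOVA with baseline as a time level is a recognised, prespecified analysis. With randomised arms, its interaction test is unbiased over repeated randomisations and keeps its type I error. That stands. A reader might infer from the regression-to-the-mean argument that the planned analysis is biased. It is not: the 0.19 cm is error conditional on an illustrative one-SE imbalance, not an expected bias.

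A reader might also take 80% against 90% as the power that this trial gives up. The documents do not support that. The figure is for one visit at unadjusted 0.05 and an assumed rho of 0.5, whereas the SAP tests the interaction first and adjusts the visit contrasts. For the interaction, the gain depends on an unknown effect shape: larger than ten points for a sustained benefit, close to nothing for a transient one. The SD and rho are absent from both documents, as is the test behind the 80%.

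One might answer that a mixed model already uses baseline. It does so only as an outcome. With the arm means free at baseline, it does not recover the covariate gain.

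Finally, the trial stopped and no inferential result is to be reported. That limits the practical effect, but 6A and 6B remain the only inferential plan, and resumption is under consideration.

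**Conclusion.** The concern holds as a point about efficiency. The direction is certain for any rho strictly between 0 and 1, whichever contrast the post-hoc tests use. The size is not certain.

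At rho 0.5 the variance of a single-visit contrast falls by 25%. Over rho 0.3 to 0.7, power on the change contrast rises from 66-95% to 84-97.5% if the stated 80% was for a raw single-visit score, or from 80% to 93-86% if it was for the change contrast. The interaction gains additionally assume equal correlations between visits.

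The finding does not show that the trial was underpowered by its own standard, or that any reported result is wrong. It is worth correcting because the gain costs almost nothing, and it applies to the plan and to any resumed study.

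**What to change.** In SAP 6A, take baseline out of the time factor. Model the four post-treatment VAS scores with group, visit, group by visit, baseline VAS, and baseline VAS by visit. A constrained longitudinal model that keeps baseline as an outcome but sets a common baseline mean for the two arms is an acceptable alternative.

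The gate must change at the same time. Once baseline has left the time factor, group by visit no longer tests for benefit: a constant benefit at all four visits gives zero interaction and would be missed. Replace the gate with a joint 4-df test of the active-minus-sham differences at the four post-treatment visits (group plus group by visit). Then take the Bonferroni-adjusted visit contrasts from the same model.

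In 6B, do the same for MFIS, PSQI, BDI, PCS, MGPQ and PVAQ, each with its own baseline score, and state the time levels used.

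The cost is a changed model statement and a few degrees of freedom: one for the baseline slope and one for each further visit's slope. No new data, visits or participants are needed. If the study resumes, the change should be dated before any unblinded comparison.
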